3.4.4 Glycaemic control

Glycaemic control will be assessed by examining levels of blood glucose concentration and glycated (glycosylated) haemoglobin A (HbA1c), or both, whenever available. Plasma glucose concentration fluctuates in response to food intake, and fasting state of patients is not always ascertainable. Haemoglobin A in the red blood cells binds to plasma glucose, becoming irreversibly glycated for the duration of the erythrocytes' lifespan. Thus, HbA1c represents a summary of glucose values over the preceding 1 – 4 months both in fasting and postprandial states. The proportion of glycated haemoglobin A is linearly related to long-term blood glucose concentration and is currently a standard measure of long-term glycaemic control.¹⁸

Results of laboratory investigations will be ascertained from the Laboratory Information Systems of the North and the Central Denmark Regions (LABKA database) in Denmark and from the GPRD's Laboratory File, in the UK. Relevant codes are provided in Appendix 1.

We will use the following measures of plasma glucose concentration (differentiating fasting from non-fasting patients whenever available):

- Mean and median change;
- Percent change from the baseline value;

- Treatment failure, defined as fasting plasma glucose level >180 mg per decilitre.

We will use the following measures of HbA1c:

- Mean and median change;
- Percent change from the baseline value;
- Results of 120-minute glucose tolerance test (standard measure of diabetes; possibly in Denmark)
- Loss of glycaemic control, defined as of HbA1c level >7.5%.

3.4.5 Biochemical parameters of disease other than glycaemic control

We will examine changes/occurrence post-baseline (see Analysis Plan for definition) of the following biochemical parameters according to the patterns of use of oral glucose-lowering drugs:

- Total cholesterol;
- LDL cholesterol;
- HDL cholesterol;
- Triglycerides;
- Haemoglobin (as a measure of anaemia);
- Alanintransaminase (ALAT as a measure of liver failure);
- Serum creatinine (as a measure of kidney failure);
- Albumin/creatinine ratio, as an early marker of vascular damage indicative or early cardiovascular damage;
- Arterial blood pressure (on a subset only if available; source: NIP data in Denmark; Additional Clinical Details File in the GPRD).

3.5 Covariates definition and measurement

Baseline comorbidities will be ascertained by examining inpatient and outpatient hospital diagnoses in the ten years preceding study enrolment and recorded in the Danish National Registry of Patients in Denmark and in the GPRD's Event File in the UK. We will use the Charlson comorbidity index to summarise comorbidities (other than diabetes) in the analysis.¹⁹

Use of prescription medication other than oral glucose lowering therapy will be ascertained based on prescription history (AUPD in Denmark; Drug File in the GPRD). Concomitant use will be defined as a record of at least one prescription for a medication that falls in one of the categories listed below between the first and the last prescription for glucose lowering therapy.

- Lipid-lowering agents (statins);

- Antihypertensive agents (ACE inhibitors, angiotensin receptor blockers, beta-blockers, calcium-channel blockers);
- Diuretics (loop, potassium sparing, thiazide);
- Nitrates;
- Antiplatelet agents.

Smoking, alcoholism, and body mass index (BMI) are available for about 70% of the patients in the GPRD's Additional Clinical Detail File (for the UK). In Denmark, these data are not generally recorded in registries, although there are diagnostic codes for obesity and alcoholism, which we will use to identify patients who were hospitalised. It may be possible to obtain data on smoking, body mass index and blood pressure at least on some members of the study population via linkage to the National Indicator Project and Danish Registry of Patients. The size of subgroup with available data on smoking, alcoholism, and BMI will not be known until data linkage.

Age and sex of the patients: in Denmark, date of birth and sex are encoded in the unique identifier that will be used to link the data; in the UK, the GPRD records the demographic data in the Registration File.

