3.4.3 Acute drug reactions

Both acute and pre-existing events will be identified in the Danish National Registry of Patients and in the Registry of Causes of Death in Denmark and in the GPRD's Event file, in the UK.

Acute drug reactions will be defined as new (first-onset) events occurring 45 days after the date of the switch to or from a rosiglitazone preparation. We will use prior hospitalization records to screen out prevalent/prior events and conditions. The exact distribution of events that may represent a potential acute drug reaction is unknown until data analysis. We will rank all recorded new events in the order of seriousness and potential of representing an acute drug reaction. Since cardiovascular side effects are a major safety concern for rosiglitazone, as a minimum, we will examine the following events:

- All-cause mortality;
- Cardiovascular mortality;
- Acute myocardial infarction;
- Cerebrovascular accident/ischemic stroke
- Pulmonary embolism;
- Deep vein thrombosis.

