3.6.3 Acute drug reactions

For patient-level endpoints, baseline will be defined as the recorded date of medication switch/addition (as reflected by a new dispensation/issue); date of the first-time prescription dispensation/issue (in first-time users) or 1 January 2000 (in prevalent users).

We will examine the number of potential drug reactions occurring within 45 days of baseline and calculate the 45-day cumulative incidence of acute drug reactions, overall and diagnosis-specific (if the data set is large enough); We will estimate risk ratios for the acute drug reactions identified using regression, while adjusting for confounding.

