Appendix 1. Codes used in data abstraction

Diagnostic codes used to Abstract the Danish National Registry of Patients and the Registry of Causes of Death

Disease/condition	ICD-8 code	ICD-10 code
Diabetes type 1	249.00; 249.06; 249.07; 249.09	E10.0, E10.1; E10.9
Diabetes type 2	250.00; 250.06; 250.07; 250.09	E11.0; E11.1; E11.9
Acute myocardial infarction	410	I21, I22, I23
Ischemic heart disease (acute and chronic)	411-414	I20, I24, I25
Congestive heart failure	427.09, 427.10, 427.11, 427.19, 428.99, 782.49;	I50, I11.0, I13.0, I13.2
Other cardiac disease	393–398, 400–404	I05–I09
Peripheral vascular disease	440, 441, 442, 443, 444, 445	I70, I71, I72, I73, I74, I77
Ischemic stroke	430-438 (cerebrovascular disease)	I63-64
Alcoholism	291, 303, 577.10, 571.09, 571.10	F10.1-F10.9, G31.2, G62.1, G72.1, I42.6, K29.2, K86.0, Z72.1
Obesity	277.99	E65-E66
Mild liver disease	571, 573.01, 573.04	B18, K70.0–K70.3, K70.9, K71, K73, K74, K76.0
Moderate to severe liver disease	070.00, 070.02, 070.04, 070.06, 070.08, 573.00, 456.00–456.09	B15.0, B16.0, B16.2, B19.0, K70.4, K72, K76.6, I85
Deep vein thrombosis	451.00	I81, I82
Pulmonary embolism	450.99	I26

ICD-8: http://www.sst.dk/Indberetning%20og%20statistik/Klassifikationer/SKS_download.aspx

ICD-10: <http://apps.who.int/classifications/apps/icd/icd10online/>

Diagnostic codes used to compute Charlson Comorbidity Index¹⁹

Disease	ICD-8 code	ICD-10 code
Myocardial infarction	410	I21;I22;I23
Congestive heart failure	427.09; 427.10; 427.11; 427.19; 428.99; 782.49	I50; I11.0; I13.0; I13.2
Peripheral vascular disease	440; 441; 442; 443; 444; 445	I70; I71; I72; I73; I74; I77
Cerebrovascular disease	430-438	I60-I69; G45; G46
Dementia	290.09-290.19; 293.09	F00-F03; F05.1; G30
Chronic pulmonary disease	490-493; 515-518	J40-J47; J60-J67; J68.4; J70.1; J70.3; J84.1; J92.0; J96.1; J98.2; J98.3
Connective tissue disease	712; 716; 734; 446; 135.99	M05; M06; M08; M09;M30;M31; M32; M33; M34; M35; M36; D86
Ulcer disease	530.91; 530.98; 531-534	K22.1; K25-K28
Mild liver disease	571; 573.01; 573.04	B18; K70.0-K70.3; K70.9; K71; K73; K74; K76.0
Diabetes type1	249.00; 249.06; 249.07; 249.09	E10.0, E10.1; E10.9
Diabetes type2	250.00; 250.06; 250.07; 250.09	E11.0; E11.1; E11.9
Hemiplegia	344	G81; G82
Moderate to severe renal disease	403; 404; 580-583; 584; 590.09; 593.19; 753.10- 753.19; 792	I12; I13; N00-N05; N07; N11; N14; N17-N19; Q61
Diabetes with end organ damage type1	249.01-249.05; 249.08	E10.2-E10.8

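### The Charlson summary in section 3.5 omits ischaemic heart disease other than infarction and pools the remaining cardiac history, so the 45-day cardiovascular risk ratios are liable to residual confounding

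*Protocol*

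**What the plan says.** Section 3.5 sets the look-back and source for comorbidity: "Baseline comorbidities will be ascertained by examining inpatient and outpatient hospital diagnoses in the ten years preceding study enrolment". It then names the summary to be used: "We will use the Charlson comorbidity index to summarise comorbidities (other than diabetes) in the analysis". Appendix 1 gives an ICD-8/ICD-10 table headed "Diagnostic codes used to compute Charlson Comorbidity Index".

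Section 3.5 names other covariates too: age, sex, statins, antihypertensives, diuretics, nitrates and antiplatelet agents. A drug counts if it was prescribed at least once "between the first and the last prescription for glucose lowering therapy". Smoking, alcohol and body mass index are used where recorded, and for Denmark "there are diagnostic codes for obesity and alcoholism, which we will use to identify patients who were hospitalised".

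For acute reactions, section 3.4.3 restricts to first-onset events: "We will use prior hospitalization records to screen out prevalent/prior events and conditions". Section 3.6.3 describes the model in one sentence, without a covariate list: "We will estimate risk ratios for the acute drug reactions identified using regression, while adjusting for confounding".

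**The concern.** The outcomes that section 3.4.3 requires as a minimum include infarction, stroke and cardiovascular death. The history most likely to confound them is cardiac, and the protocol gives reasons to expect that history to differ between treatment groups. Its background section reports the 2007 regulatory advice to respect restrictions in patients with cardiac disease. Section 3.6.2 names ischaemic heart disease and peripheral vascular disease as contraindications added in 2008. The background also records the opposite possibility, that people with an indication for rosiglitazone may start from a higher cardiovascular risk.

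A comorbidity score that gives nothing for angina or chronic coronary disease cannot adjust for it. A score that adds heart failure to unrelated conditions adjusts for heart failure only loosely. The result at stake is the safety comparison around switching. Confounding could create an apparent harm, or it could hide a real one. The limitations in section 4 mention residual confounding by lifestyle factors but not by cardiac disease.

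**Working it through.** **1. Code comparison.** Both lists are in Appendix 1.

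| Condition | ICD-8 | ICD-10 | Row in the Charlson table? |
|---|---|---|---|
| Infarction | 410 | I21-I23 | Yes |
| Other ischaemic heart disease | 411-414 | I20, I24, I25 | No |
| Heart failure | 427.09, 427.10, 427.11, 427.19, 428.99, 782.49 | I50, I11.0, I13.0, I13.2 | Yes, pooled |
| Peripheral vascular disease | 440-445 | I70-I74, I77 | Yes, pooled |
| Cerebrovascular disease | 430-438 | I60-I69, G45, G46 | Yes, pooled |

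The codes for other ischaemic heart disease do not overlap with the Charlson table in either ICD version. The complete omission concerns that condition alone. Heart failure and peripheral vascular disease are present, but merged with rows such as ulcer disease and chronic pulmonary disease.

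**2. Effect of the first-onset screen.** Prior infarction is removed from the infarction analysis, so the Charlson infarction item carries no information there. The screening sentence does not clearly reach coronary disease without infarction.

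**3. The drug proxies.** Nitrates and antiplatelet agents mark coronary disease to some extent. Their window runs to the last glucose-lowering prescription, so a drug first prescribed because of a study infarction would still count as a covariate. The UK antiplatelet list also has no code for aspirin alone.

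**4. Size, on assumed inputs.** The protocol gives no prevalence, event rate or risk ratio, so there is no stated figure to reproduce. Take a true drug ratio of 1.00. Let p1 and p0 be the prevalence of non-infarction ischaemic heart disease in users and comparators, and RR its effect on the outcome. The apparent ratio is

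B = [1 + p1(RR − 1)] / [1 + p0(RR − 1)].

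The last two columns adjust for an error-prone drug proxy (specificity 90%, sensitivity 50% / 80%), standardised to the users.

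| p1 | p0 | B, RR = 2 | B, RR = 3 | Proxy-adjusted, RR = 2 | Proxy-adjusted, RR = 3 |
|---|---|---|---|---|---|
| 0.05 | 0.20 | 1.05/1.20 = 0.875 | 1.10/1.40 = 0.786 | 0.894 / 0.925 | 0.816 / 0.865 |
| 0.10 | 0.20 | 1.10/1.20 = 0.917 | 1.20/1.40 = 0.857 | 0.930 / 0.951 | 0.879 / 0.913 |
| 0.15 | 0.20 | 1.15/1.20 = 0.958 | 1.30/1.40 = 0.929 | 0.965 / 0.976 | 0.940 / 0.958 |
| 0.20 | 0.20 | 1.000 | 1.000 | 1.000 | 1.000 |
| 0.25 | 0.20 | 1.25/1.20 = 1.042 | 1.50/1.40 = 1.071 | 1.034 / 1.023 | 1.058 / 1.040 |

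One proxy-adjusted cell in full (p1 = 0.05, p0 = 0.20, RR = 3, sensitivity 50%):

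- Proxy-positive users: 0.05×0.5 + 0.95×0.1 = 0.12. Proxy-negative users: 0.88.
- Disease prevalence among comparators: 0.10/0.18 = 0.556 if proxy-positive, 0.10/0.82 = 0.122 if proxy-negative.
- Expected risk with the comparators' disease pattern: 0.12×(1 + 2×0.556) + 0.88×(1 + 2×0.122) = 1.348.
- Users' risk: 1 + 0.05×2 = 1.10. Ratio: 1.10/1.348 = 0.816.

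The span is 0.79-1.07 without proxy adjustment and 0.82-1.06 with it. The second span treats the proxy as measured before baseline, which section 3.5 does not ensure.

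**The case against.** The strongest reply is that the protocol never says Charlson is the sole adjustment. A reader might infer that from section 3.5, but the same section lists cardiac drugs, age, sex, and obesity and alcoholism codes, and 3.6.3 leaves the covariate list open. A separate analysis plan could add ischaemic heart disease. This stands: one cannot say that the ratios will stay confounded, only that the stated method leaves them liable to it. It does not dispose of the point, because naming Charlson as the comorbidity summary is a stated choice, not a detail left for later.

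Further stronger readings also go beyond the document:

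- *The gap is shown for the whole study.* The Charlson table is ICD-coded and so shows the gap for Denmark. No Read-code version is given. The UK supplies about 20,000 of 22,400 rosiglitazone users (20,000/22,400 = 89%), and its appendix has a broad cardiovascular group that includes angina and ischaemic heart disease. For the UK, the content of the index is unknown rather than shown to be deficient.
- *The bias inflates the rosiglitazone risk.* The contraindications suggest less ischaemic heart disease among users; the background suggests that users may have higher prior risk. The direction is not determined.
- *Heart failure counts the same as an ulcer.* That depends on the index weights, which the protocol does not print. The objection to pooling does not need them.
- *Ischaemic heart disease steered prescribing throughout.* It is listed as an additional contraindication only in 2008, after Period 1 had ended, although some cardiac restriction is mentioned for 2007.

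**Conclusion.** The point holds in moderate form. On the protocol's own code table, the named comorbidity summary contains no ischaemic heart disease other than infarction and merges the other cardiac conditions with non-cardiac ones. The protocol itself links cardiac disease to rosiglitazone prescribing and studies cardiovascular outcomes. Residual confounding of the 45-day risk ratios is therefore likely enough to justify a change, but it is not certain and its sign is unknown. The drug covariates reduce it only partly and are poorly timed.

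The size rests wholly on assumed prevalences (5-25% against 20%) and an assumed risk ratio of 2-3. If the disease is balanced between groups, this source of bias vanishes. If it is rarer among users, a real excess risk could be understated.

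**What to change.** In 3.5 and 3.6.3, state that baseline ischaemic heart disease, heart failure and peripheral vascular disease enter the acute-reaction models as separate covariates in both countries, with prior infarction and prior stroke added where the first-onset rule has not removed them. Use the ICD and Read codes already in Appendix 1, and keep a Charlson score of the remaining conditions. For the UK, ischaemic heart disease has to be picked out of the broader cardiovascular Read-code group. Section 3.4.1 extracts these histories for rosiglitazone users, so the same extraction must also be run for comparators. Where Danish events are too few for separate terms, put the same indicators into a propensity or disease-risk score. In section 4, name residual cardiac confounding as a limitation.

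The cost is wording in three sections, code lists applied to more patients, and a few more model terms. No new data source is needed.

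### Co-medication is counted over the whole glucose-lowering treatment history instead of up to the index date, and the comorbidity look-back hangs on an undefined study enrolment date

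*Protocol*

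**What the plan says.** Section 3.5 of the protocol fixes two covariates.

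- **Co-medication.** "Concomitant use will be defined as a record of at least one prescription for a medication" in one of five listed classes, falling "between the first and the last prescription for glucose lowering therapy". One prescription is enough, and the window has no link to a switch.
- **Comorbidity.** It is ascertained from "inpatient and outpatient hospital diagnoses in the ten years preceding study enrolment", and "We will use the Charlson comorbidity index to summarise comorbidities (other than diabetes) in the analysis". The protocol does not define study enrolment. Under sections 3.1 and 3.3, cohort membership rests on two or more oral glucose-lowering prescriptions between 1 January 2000 and 1 January 2011, not on a switch.

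Section 3.6.3 sets a different time zero for patient-level endpoints: "baseline will be defined as the recorded date of medication switch/addition", or the first prescription in first-time users, or 1 January 2000 in prevalent users. It then plans to "calculate the 45-day cumulative incidence of acute drug reactions" and to estimate risk ratios by regression with adjustment for confounding. No section re-anchors either covariate to that baseline.

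**The concern.** A confounder has to be fixed before the exposure contrast begins. The co-medication flag is not: its window stays open through the switch, through the 45-day outcome period and on to the last glucose-lowering prescription. Acute myocardial infarction is a named outcome in section 3.4.3. A nitrate or antiplatelet started because of a non-fatal infarction after the switch would be entered as a confounder of that infarction. Patients who stay on treatment longer also have more time to be flagged, so the flag partly records later treatment duration and survival.

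The comorbidity question is related. If the look-back ends at cohort entry, disease that arose between entry and a late switch is not in the Charlson index, although such disease may be part of the reason for switching.

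At stake are the adjusted risk ratios for the fourth specific aim, acute reactions after switching to or from rosiglitazone.

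**Working it through.** The protocol gives no figure on this point to reproduce. Step 1 uses its own dates. Steps 2 and 3 are illustrations whose inputs are all assumed.

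**1. Dates** (sections 3.1 and 3.6.1; years = days / 365.25)

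Time in which co-medication still counts after a 45-day outcome window, up to 1 January 2011:

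- switch on 1 July 2000: 3836 − 45 = 3791 days, 10.4 years
- switch on 23 May 2007: 1319 − 45 = 1274 days, 3.5 years
- switch on 23 September 2010: 100 − 45 = 55 days

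The opportunity to be flagged after the outcome thus depends on calendar date. Comparison groups that switch at different times will differ in it.

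Gap from a cohort entry on 1 January 2000 to a switch:

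- 23 May 2007: 2699 days, 7.4 years
- 24 January 2008: 2945 days, 8.1 years
- 23 September 2010: 3918 days, 10.7 years
- 1 January 2011: 4018 days, 11.0 years

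**2. Fatal outcome, true risk ratio 1.00**

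Assumed: equal groups, 45-day risk 0.5% in both, 30% co-medicated at the switch in both, later initiation 15 per 100 person-years, later treatment exponentially distributed with mean 1 year in one group and 5 in the other.

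- Flagged share of survivors = 0.30 + 0.70 × (1 − 1/(1 + 0.15 × mean years)). This gives 0.391 for 1 year and 0.600 for 5 years.
- Flagged share of deaths within 45 days: about 0.305 in both groups.
- Flagged stratum: risk ratio ≈ 0.600/0.391 = 1.53.
- Unflagged stratum: 0.400/0.609 = 0.66.
- Mantel-Haenszel: (0.305 × 0.600/0.991 + 0.695 × 0.400/1.009) / (0.305 × 0.391/0.991 + 0.695 × 0.609/1.009) = 0.460/0.540 = 0.85.

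The unadjusted ratio here is 1.00, so the adjustment itself creates the error.

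**3. Non-fatal outcome**

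Assumed: equal groups, 40% co-medicated at the switch in both, 45-day risk 0.5% without co-medication and twice that with it. Of unmedicated cases, 70% or 95% start a drug after the event. Unmedicated non-cases start later at the rates shown (group 1 / group 0).

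| Later uptake in non-cases | True 1.00: 70% / 95% | True 1.50: 70% / 95% |
|---|---|---|
| 50% / 50% | 1.00 / 1.00 | 1.50 / 1.50 |
| 70% / 30% | 0.82 / 0.73 | 1.23 / 1.09 |
| 30% / 70% | 1.22 / 1.38 | 1.82 / 2.06 |
| 60% / 10% | 0.72 / 0.63 | 1.08 / 0.94 |
| 10% / 60% | 1.39 / 1.60 | 2.08 / 2.39 |

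One cell worked through (true 1.00, 70% / 30%, 95%), per person in each group:

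- Flagged cases: 0.004 + 0.95 × 0.003 = 0.00685 in each group. Unflagged cases: 0.00015.
- Flagged people: 0.8208 and 0.5820. Unflagged people: 0.1793 and 0.4181.
- Mantel-Haenszel numerator: 0.00685 × 0.5820/1.4027 + 0.00015 × 0.4181/0.5973 = 0.002947.
- Denominator: 0.00685 × 0.8208/1.4027 + 0.00015 × 0.1793/0.5973 = 0.004053.
- Ratio: 0.73.

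Stratifying instead on co-medication at the switch returns the true value in every row.

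**The case against.** **Enrolment may mean the index date.** Section 3.5 speaks of baseline comorbidities, and section 3.6.3 defines baseline as the switch, addition or first use. On that reading the comorbidity gap disappears. For first-time users whose baseline is their first prescription the two dates may coincide anyway. This stands: a reader might infer that comorbidity is definitely frozen years before the switch, but the documents support only an undefined term whose plain reading has that effect.

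**The first-onset screen covers part of the gap.** A reader might argue that a myocardial infarction in 2007 that prompted a 2008 switch goes unadjusted. Section 3.4.3 limits reactions to first-onset events and removes prior ones, so that patient would not contribute a first infarction. The gap matters for outcomes the screen does not cover, mortality above all.

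**Early deaths are not unflagged by construction.** At an assumed 10 initiations per 100 person-years, the chance of a flag is 1 − exp(−0.1 × 45/365.25) = 1.2% over 45 days and 1 − exp(−1) = 63% over ten years. That contrast describes a first-time user who dies early. A switcher brings in all the time since the first glucose-lowering prescription.

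**The adjustment set is not listed.** Section 3.6.3 says only that confounding will be adjusted for. Section 3.5 commits the Charlson index to the analysis expressly, and the co-medication flag only by standing in a section on covariates. It is therefore an inference that every adjusted risk ratio is affected. The model's covariate list may properly sit in an analysis plan.

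None of this answers the co-medication definition, which the protocol itself fixes and which runs past the outcome window.

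**Conclusion.** The co-medication definition is wrong as written for any analysis that starts at the section 3.6.3 baseline. It uses post-index information in all patients and, for non-fatal outcomes, can use information produced by the outcome. If the flag enters the 45-day regressions, it can bias the risk ratios in either direction.

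The size cannot be derived from the documents. The figures of 0.85, and of 0.63 to 1.60, for a true 1.00 rest wholly on assumed inputs, and the illustrated bias vanishes when later uptake is equal in the two groups. Equality should not be presumed, since the time left for a flag falls from 10.4 years to 55 days between the earliest and the suspension-date switches.

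The comorbidity point is conditional. If study enrolment means cohort entry, up to about 10.7 to 11 years of diagnoses before a late switch are missed for outcomes outside the first-onset screen. If it means the index date, only the wording needs repair.

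The utilisation, contraindication and off-label aims are descriptive and unaffected.

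**What to change.** In section 3.5:

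- Define co-medication as at least one prescription in a fixed window ending the day before each index date (switch, addition or first use). The window length is the investigators' choice and should be stated.
- State that the ten-year look-back for comorbidity and the Charlson index ends the day before that same index date, in place of the reference to study enrolment.
- Recompute both for every switch a patient contributes.
- State that no information from after baseline is used for adjustment.

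The cost is a few sentences and re-programmed covariates. No new data are needed: section 6 describes dated prescription records in both countries, and the ten-year look-back already requires dated diagnoses.
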